TITLE: Combined effect of tDCS and motor or cognitive activity in patients with Alzheimer's Disease: a proof-of-concept pilot study

NCT Number: NCT06619795

02/10/2024

The aim of this study will be to evaluate the effectiveness of combining tDCS with motor or cognitive activities on cognitive functions in patients with AD. A secondary aim will be to investigate whether tDCS will have a different impact when combined with motor versus cognitive activities.

Materials and Methods

The study will be a double-blind randomized controlled trial (RCT) that will compare the effects of anodal and sham tDCS combined with motor or cognitive activity on cognitive performance in AD patients. The research team will consist of "evaluators" and "treatment providers." The neuropsychologist evaluator will be responsible for measuring outcomes and will remain unaware of the group assignments. Additionally, to assess the presence of a placebo effect or the absence of an effect from the anodal stimulation, and to reduce potential bias, participants will also be kept unaware of the type of stimulation being administered. In contrast, the treatment providers, including neuropsychologists and physiotherapists, will be informed about the treatment but will not know the type of tDCS stimulation used (anodal or sham) (Cotelli et al., 2014).

Participants

Patients with AD will be recruited from the Mons. A. Mazzali Foundation (Mantua). The inclusion criteria will be: Mini Mental State Examination (MMSE) >15, good level of compliance, treatment with acetylcholinesterase inhibitors (e.g., donepezil, rivastigmine), and no modifications to medication in the last four months. The exclusion criteria will be: behavioral disorders (e.g., aggressiveness), alcohol abuse, orthopedic conditions with a risk of falls, respiratory disorders, uncorrected severe auditory or visual deficits, history of epileptic fits, use of anti-epileptic medication, metallic body implants, pacemaker, and psychiatric, neurological, systemic, or metabolic disorders.

Following a simple software-generated randomization scheme (www.randomization.org), patients will be allocated to one of four groups after the baseline evaluation. Unbalanced randomization will be applied. The randomization list will not be disclosed to the assessors or treatment providers but will be known only to the principal investigator (CF).

Treatment procedures

The real tDCS groups will receive anodal stimulation combined with either motor activity (MotA) or cognitive activity (CogA). The sham tDCS groups will receive sham stimulation combined with motor activity (MotS) or cognitive activity (CogS).

Each group will undergo 45 minutes of activity, with the first 15 minutes performed simultaneously with tDCS stimulation. Treatments (45 minutes) will be administered for two weeks, five times per week (Cotelli et al., 2014)..

During the study, participants will not engage in any other motor or cognitive activities.

Motor activity

A standardized sequence of motor exercises will be established. A physiotherapist will conduct the individual motor activity, which will include moderate-intensity endurance and resistance training. Each session will begin with a 5-minute warm-up and conclude with a 5-minute cool-down, including active joint mobilization. Subsequently, patients will engage in endurance exercises, which will be

randomly ordered and divided among cycling on a cycle ergometer, walking on a platform, and arm cranking on a specialized ergometer (Fonte et al., 2019).

Cognitive activity

A neuropsychologist will conduct individual cognitive activities, focusing on stimulating residual cognitive abilities, particularly memory. The cognitive stimulation will be tailored to the severity of each patient's cognitive decline. Each session will begin with an orientation exercise, followed by oral and paper-and-pencil tasks targeting specific cognitive functions. These exercises will aim to encourage natural reminiscence processes while also focusing on the present, enhancing social interaction and mood. Multisensory stimulation will also be incorporated.

The structure of the neuropsychological treatment will be modeled after a study conducted by Spector et al. in 2003, which involved 201 dementia patients (Spector et al., 2003). This approach demonstrated positive outcomes in several cognitive domains, as well as improvements in quality of life, while maintaining a high level of feasibility and adaptability (Fonte et al., 2019; Spector et al., 2003).

tDCS procedure

The tDCS stimulation will be performed using a BrainSTIM stimulator (EMS). A pair of saline-soaked electrodes will be placed and secured on the patients. The anode (25 cm^2 , 5x5 cm) will be positioned over the left dorsolateral prefrontal cortex (DLPFC) following the 10–20 system (F3-F7 position), and the cathode (35 cm^2 , 7x5 cm) will be placed above the shoulder on the opposite side. The stimulation procedure will be adapted to align with the prevalent literature, as the DLPFC montage is widely used (Pillonni et al., 2022; Fonte et al., 2021). The intensity of the stimulation will be set at 2mA and applied for the first 15 minutes of either cognitive or motor activity (45 minutes total).

The electrode placement and parts of the stimulation procedure will follow the protocol described by Cotelli and colleagues in 2014 (Cotelli et al., 2014). To ensure safety, the current density of the active electrode will be kept within the limits established by Poreisz and collaborators in 2007 and Nitsche and collaborators in 2008. In the sham condition, the current will be turned off 10 seconds after the stimulation starts and turned back on during the final 10 seconds, so that participants will be unable to discern whether the stimulation is real or sham (Poreisz et al., 2007; Nitsche et al., 2008).

Evaluation procedures

Primary and secondary outcomes will be measured by the same blinded examiner. Patients will be evaluated before treatment (T0), immediately after treatment (T1), and at a one-week follow-up (T2). Cognitive assessments will be conducted in a single session lasting one hour. The tests used in the assessment are described below.

- Primary Outcome

The primary outcome will be the Mini Mental State Examination (MMSE), used to assess global cognitive impairment (Folstein et al., 1975).

- Secondary Outcomes

The secondary outcomes will include:

- Picture Recognition (PR) is a subtest of the Rivermead Behavioral Memory Test-3, an ecological memory battery resembling everyday tasks, with the aim to measure daily memory function (Beschin et al., 2013).
- Digit Span Test- Forward (DSF), used to measure span of immediate verbal recall. The examiner presents digits verbally at a rate of one per second (Monaco et al., 2013).
- Digit Span Test- Backward (DSB), used to measure working memory (Monaco et al., 2013).
- Phonemic Fluency Test (PFT), used to measure processing speed, language production and executive functions (Zappalà et al., 1995).
- Visual Search Test (VST), to assess visual-selective attention (Spinnler & Tognoni, 1987).
- Sustained Attention to Response Test (SART): used to evaluate sustained attention and control inhibition. In the test, participants view a computer monitor on which a random series of single digits are presented at the regular rate of 1 per 1.15 seconds (Robertson et al., 1997).
- Neuropsychiatric Inventory (NPI) to evaluate the presence, frequency and severity of behavioral disorders (Cummings et al., 1994).

Statistical analysis

Data from all randomized patients will be assessed. The Kruskal-Wallis test will be used to measure baseline homogeneity for all outcome measures across the four groups. The Mann-Whitney U test will be employed to examine the effects of tDCS by comparing MotA+CogA versus MotS+CogS between T1 and T0 (T1-T0) and between T2 and T0 (T2-T0). Further analysis will investigate differences in performance between the MotA and CogA groups from T1 to T0 (T1-T0) and from T2 to T0 (T2-T0). The alpha level for significance will be set at $P < 0.05$.

Statistical analysis will be conducted using the Statistical Package for Social Science (SPSS) for Macintosh, version 26.0 (IBM SPSS Inc, Armonk, NY, USA).

To determine the sample size, based on the study by Khedr and colleagues, an effect size of 1.15 will be calculated using G*Power 3.1.9.4 software. With an effect size of 1.15, an alpha of 0.01, and a power of 0.90, a total of 48 patients will be required to detect a significant treatment effect (Khedr et al., 2019).

REFERENCES

3. Khedr, E. M.; Salama, R. H.; Abdel Hameed, M.; Abo Elfetoh, N.; Seif, P. Therapeutic Role of Transcranial Direct Current Stimulation in Alzheimer Disease Patients: Double-Blind, Placebo-Controlled Clinical Trial. *Neurorehabilitation and neural repair* 2019, 33(5), 384–394. doi:10.1177/1545968319840285.
4. OSF Registries. Available online: <https://osf.io> (accessed on 30 August 2024).

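### Simple, unbalanced randomization of 48 patients to four groups, with no ratio, reason or blocking, leaves group sizes to chance and loses precision for no stated benefit

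*Combined protocol and SAP*

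**What the plan says.** The Participants section describes allocation to MotA, CogA, MotS and CogS after the baseline evaluation: "Following a simple software-generated randomization scheme", and then "Unbalanced randomization will be applied". The list is known only to the principal investigator. No ratio, favoured group, reason for imbalance, blocking or stratification appears anywhere.

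The Statistical analysis section gives the sample size: "With an effect size of 1.15, an alpha of 0.01, and a power of 0.90, a total of 48 patients will be required". It names no test, sidedness or allocation ratio for that calculation. The planned test is a Mann-Whitney U test to "examine the effects of tDCS by comparing MotA+CogA versus MotS+CogS", with MotA versus CogA as a further comparison. The significance threshold for the analysis is 0.05, while the sample-size sentence uses "an alpha of 0.01".

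**The concern.** Nobody could generate the intended randomization list from this text, because the degree and direction of the imbalance are unknown. At a fixed total and equal variances, moving the anodal and sham totals apart can only reduce the power of the pooled comparison. The documents name nothing gained in return.

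Simple randomization adds chance imbalance on top of whatever ratio is meant. With four groups and 48 patients, that chance is not negligible. It matters most for the secondary aim, whether tDCS acts differently with motor than with cognitive activity. That aim depends on single groups of about 12, not on pooled arms of about 24. Because the sample-size sentence is silent on ratio, a reader also cannot tell whether 48 allows for unequal groups.

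**Working it through.** **Inputs.** From the Statistical analysis section: d = 1.15 (taken as the standardized difference for the pooled comparison), alpha 0.01 for sizing and 0.05 for analysis, power 0.90, N = 48, Mann-Whitney test. From the Participants section: four groups, simple and unbalanced. Sidedness and ratio are not given, so ranges are shown.

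**1. The plan's own figure.** The normal approximation at two-sided alpha 0.01 gives n per arm = 2(2.576 + 1.282)²/1.15² = 22.5, so 23 per arm and N = 46. The noncentral t with equal arms gives N = 50 two-sided and 44 one-sided. The stated 48 lies between the two two-sided results. A one-sided t-test at 2:1 gives 32 + 16 = 48 exactly, so an unreported ratio could already be in the figure.

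**2. Power of the pooled comparison at N = 48.** The noncentrality is d√(n₁n₂/(n₁+n₂)). For the Mann-Whitney test, the sample sizes are multiplied by the efficiency 3/π ≈ 0.955. At 24/24 the noncentrality is 1.15 × √12 = 3.98 for t and 1.15 × √(0.955 × 12) = 3.89 for Mann-Whitney.

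| Anodal/sham split | t, two-sided 0.01 | Mann-Whitney, two-sided 0.01 | Mann-Whitney, one-sided 0.01 | Mann-Whitney, two-sided 0.05 |
|---|---|---|---|---|
| 24/24 | 0.897 | 0.879 | 0.926 | 0.968 |
| 30/18 | 0.873 | 0.853 | 0.907 | 0.958 |
| 32/16 | 0.852 | 0.830 | 0.891 | 0.948 |
| 36/12 | 0.773 | 0.748 | 0.826 | 0.909 |

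The unequal splits are illustrations. Direct simulation of the Mann-Whitney test at two-sided 0.01 gave 0.865 to 0.877 at 24/24 and 0.72 to 0.73 at 36/12, close to the formula. Averaged over the chance splits of simple randomization with equal probabilities, Mann-Whitney power at two-sided 0.01 is 0.870, against 0.879 for a fixed 24/24.

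**3. Group sizes under simple randomization.** These are multinomial draws of 48 into four groups.

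| Probabilities | Smallest group ≤ 8 | ≤ 6 | ≤ 5 | ≤ 4 |
|---|---|---|---|---|
| Equal | 45% | 11% | 4% | 1% |
| 2:2:1:1, anodal larger (assumed) | 87% | 52% | 32% | 16% |

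With equal probabilities the anodal total is binomial(48, 0.5), with a 95% range of 17 to 31.

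**4. Precision of the comparisons between activities.** The variance of MotA versus CogA is proportional to 1/n₁ + 1/n₂. The variance of the four-group contrast (the tDCS effect with motor minus the tDCS effect with cognitive activity) is proportional to the sum of 1/n over all four groups. At 12 per group these sums are 2/12 = 0.167 and 4/12 = 0.333. Averaged over simple equal-probability lists, both rise by about 7%. With fixed groups of 16, 16, 8 and 8 the four-group sum is 2/16 + 2/8 = 0.375, up 12.5%. With chance variation added, the rise is about 25%.

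**5. Power of MotA versus CogA.** At d = 1.15 and two-sided alpha 0.05, Mann-Whitney power is 0.75 at 12/12 and 0.55 at 8/8.

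**The case against.** A reader might infer that the randomization leaves the stated 0.90 power undelivered, since no split of 48 reaches 0.90 with the Mann-Whitney test at two-sided alpha 0.01. The documents do not support that, for four reasons.

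- Sidedness is not stated. One-sided, the Mann-Whitney test has 0.93 at 24/24 and 0.91 at 30/18.
- The analysis threshold is 0.05. There, power stays at 0.909 even at 36/12.
- The shortfall at 24/24 (0.879, or 0.897 for a t-test) comes from the choice of test and from rounding, not from the allocation. Balanced allocation would not remove it.
- The imbalance may lie only between motor and cognitive activity. The pooled test then loses nothing to it. Unbalanced may even mean no more than unrestricted allocation, with no ratio to report.

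A reader might also infer that MotA versus CogA rests on the smallest groups. Under a 2:2:1:1 ratio favouring anodal stimulation, those two would be the larger groups, at about 16 each. The loss would then fall on the four-group contrast. The secondary aim implies that contrast, but the plan does not specify a test of it.

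Finally, this is a proof-of-concept pilot and MotA versus CogA is a further analysis. With equal probabilities, a group of 6 or fewer is a tail event. All of this stands. It limits the power argument, but it does not supply a ratio, a reason or any control over group sizes.

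**Conclusion.** The point holds as an inexpensive improvement to the design. As written, the plan leaves group sizes to chance and accepts imbalance for no stated benefit. With equal probabilities the cost is modest on average: about 7% more variance for the activity comparisons and about 1 point of power for the pooled test. There is also an 11% chance that some group has 6 patients or fewer. With a deliberate 2:1 imbalance between anodal and sham the cost is larger, but that ratio is an assumption.

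The 0.90 power can be neither confirmed nor refuted for the planned allocation. The answer turns on the unstated ratio and sidedness and on which of the two alphas applies. The power figures assume that 1.15 is a standardized difference for the pooled comparison and that the data are roughly normal. The group-size figures depend on neither alpha nor sidedness.

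**What to change.** Replace the two randomization sentences with wording such as: *Patients will be allocated 1:1:1:1 to MotA, CogA, MotS and CogS using permuted blocks of randomly varying size. Block sizes and the list will be concealed from evaluators and treatment providers.* If an unequal ratio is intended, state the ratio and the reason, and keep the blocks.

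Restate the power for that ratio, the Mann-Whitney test, a stated sidedness and one alpha used for both sample size and analysis. With 24/24 this is about 0.88 at two-sided 0.01, 0.93 at one-sided 0.01, or 0.97 at two-sided 0.05.

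The cost is a new list and a few sentences, with no extra patients. The downside is slightly more predictable allocation, limited by the varying block sizes and the concealed list. At two-sided 0.01 the stated power would also be slightly below 0.90.

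### The anodal-versus-sham test on MMSE uses unadjusted change from T0; naming a T0-adjusted rank test in advance would be a cheap improvement, not the correction of an error

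*Combined protocol and SAP*

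**What the plan says.** In the combined protocol and SAP, Evaluation procedures names MMSE as the primary outcome, measured at T0, T1 and T2. Statistical analysis gives one test for the stimulation effect: "The Mann-Whitney U test will be employed to examine the effects of tDCS by comparing MotA+CogA versus MotS+CogS", on T1-T0 and on T2-T0. It names no covariate, effect estimate or confidence interval.

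Apart from the subtraction, baseline appears once: "The Kruskal-Wallis test will be used to measure baseline homogeneity for all outcome measures across the four groups". Nothing is said about what follows from either result of that test.

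Under Participants, randomization is simple and software-generated. The section adds "Unbalanced randomization will be applied" without a ratio and mentions no stratification on MMSE. Entry requires "Mini Mental State Examination (MMSE) >15".

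The sample size statement reads "With an effect size of 1.15, an alpha of 0.01, and a power of 0.90, a total of 48 patients will be required". It does not say whether 1.15 is standardized to the SD of the score or of the change. The analysis alpha is set separately at 0.05.

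**The concern.** A change score gives baseline a slope of exactly 1. If follow-up MMSE rises with T0 MMSE at some other slope b, subtraction removes too much of a chance baseline difference (b < 1) or too little (b > 1). When b < 1, the arm that starts lower is favoured; when b > 1, the arm that starts higher is.

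With about 48 patients and simple randomization, moderate imbalance on MMSE is quite possible, and readers will judge the one allocation that occurred. The Kruskal-Wallis test does not protect against this: a non-significant result does not show balance, and a significant one changes nothing in the analysis. If the groups visibly differ at T0, the plan has no adjusted analysis ready, and one added later would be post hoc.

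**Working it through.** **The plan's own figure.** For d = 1.15, alpha 0.01 two-sided (sidedness assumed) and power 0.90, the normal approximation gives 2 × (2.576 + 1.282)² / 1.15² = 22.5, so 23 per group and 46 in total. A two-sided t-test has power 0.897 at 24/24 and needs 50. The stated 48 is within 2 of both.

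**Assumptions, because the documents are silent.** r ranges from 0.5 to 0.95; SDs are equal at T0 and follow-up unless stated, so b = r; allocation is 24/24, with 32/16 as an unbalanced example; tests are two-sided.

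**Chance of imbalance.** The SE of the T0 difference D is sqrt(1/24 + 1/24) = 0.289 SD, so P(|D| > 0.5 SD) = P(|Z| > 1.73) = 0.083, or 0.042 in one direction. At 32/16 the SE is 0.306 and the probability 0.102.

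**Remainder.** The mean-change contrast is shifted by -(1 - b)D. For D = -0.5 SD (anodal lower) and no true effect, with rejection rates at nominal 0.05 from 40,000 simulated trials per setting:

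| | r = 0.5 | 0.7 | 0.9 | 0.95 |
|---|---|---|---|---|
| Shift, (1 - r) × 0.5, in T0 SDs | 0.25 | 0.15 | 0.05 | 0.025 |
| Mann-Whitney on change | 0.096 | 0.079 | 0.057 | 0.053 |
| Share of planned effect if 1.15 is in change SDs | 22% | 17% | 10% | 7% |
| Share of planned effect if 1.15 is in raw-score SDs | 22% | 13% | 4% | 2% |

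In the same runs ANCOVA rejects in 0.049 to 0.051 and Mann-Whitney on T0-adjusted residuals in 0.045 to 0.047. The first share divides the shift by 1.15 × sqrt(2(1 - r)); at r = 0.7 that is 0.15 / 0.891 = 17%. The second divides by 1.15; at r = 0.7 that is 0.15 / 1.15 = 13%.

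**Unequal SDs.** If the follow-up SD is 1.2 times the T0 SD, then b = 1.2r. The remaining share of D, 1 - 1.2r, is 0.40, 0.16, 0.04, -0.08 and -0.14 at r = 0.5, 0.7, 0.8, 0.9 and 0.95. It nearly vanishes at r = 0.8 and changes sign above that.

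**Over all randomizations.** Simulated type I error is 0.045 to 0.053 for Mann-Whitney on change, 0.043 to 0.053 for ANCOVA and 0.047 to 0.056 for the residual test.

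**Power.** Illustrative effect of 0.6 change SDs, 24/24, alpha 0.05, equal SDs, 20,000 trials per setting:

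| Errors | Test | r = 0.5 | 0.7 | 0.8 | 0.9 | 0.95 |
|---|---|---|---|---|---|---|
| Normal | Mann-Whitney on change | 0.50 | 0.50 | 0.50 | 0.50 | 0.50 |
| Normal | ANCOVA | 0.64 | 0.59 | 0.56 | 0.54 | 0.53 |
| Normal | Mann-Whitney on residuals | 0.62 | 0.57 | 0.54 | 0.52 | 0.51 |
| t, 3 df | Mann-Whitney on change | 0.65 | 0.70 | 0.72 | 0.75 | 0.75 |
| t, 3 df | ANCOVA | 0.71 | 0.67 | 0.65 | 0.63 | 0.61 |
| t, 3 df | Mann-Whitney on residuals | 0.85 | 0.81 | 0.79 | 0.77 | 0.75 |

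Other settings covered the 1.2 SD ratio, 32/16 allocation, and integer scores with T0 truncated to 16-30. Over all of these, the residual test ranged from 0.010 below Mann-Whitney on change (0.655 against 0.665; integer scores, heavy tails, r = 0.95) to 0.196 above it (0.849 against 0.653; heavy tails, r = 0.5).

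At the planned 1.15, read in change SDs, power at alpha 0.05 is 0.97 for Mann-Whitney on change and 0.97 to 0.99 for ANCOVA.

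**The case against.** The strongest reply is that nothing here is wrong. A rank test on change is a defensible choice for a bounded score in a small proof-of-concept pilot. It holds its size, and at the planned effect with alpha 0.05 adjustment adds almost nothing. T0 and T1 are about two weeks apart with the same examiner, so r may be high. **All of this stands except the last step:** the documents give no r, so neither end of the range is established.

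A second reply is that the usual remedy, ANCOVA, can do worse than the plan. This also stands. With heavy-tailed errors at r = 0.9, its power is about 0.62 to 0.63, against 0.74 to 0.75 for Mann-Whitney on change. That counts against ANCOVA as the only test but not against adjustment: the residual Mann-Whitney test reaches about 0.76 to 0.77 there.

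A reader might infer that the planned test is biased or inflates the type I error. The plan does not support that: over randomizations the error rate is about 0.05, and the raised rates apply only given an imbalance. A reader might also infer that some of every baseline difference always survives subtraction. It does not when b = 1.

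**Conclusion.** The point holds as a suggestion for improvement. The plan names no T0-adjusted comparison for MMSE, and the unadjusted change score leaves -(1 - b)D in the mean-change contrast unless b = 1. With equal SDs the issue is material at r of 0.5 to 0.7 and small at 0.9 or more.

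The figure of about 0.10 belongs to the low end of the assumed range. It is conditional on anodal starting 0.5 SD lower, and imbalances beyond that in this direction occur in about 4% of 24/24 trials. It should not be quoted as the trial's false-positive rate.

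The omission itself is certain from the text. Its importance depends on r, the SDs, the allocation ratio and the units of the 1.15, none of which the documents state.

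**What to change.** Before unblinding, state that the anodal-versus-sham comparison on MMSE will be a Mann-Whitney test on the residuals of T1 MMSE regressed on T0 MMSE and activity (motor or cognitive), with T2 handled likewise, and that it will be used whatever the observed balance. Report beside it, as the effect estimate, the adjusted MMSE difference with 95% CI from ANCOVA on stimulation, activity and T0. Keep Mann-Whitney on change as a sensitivity analysis.

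The cost is a few sentences in Statistical analysis. T0 is already collected, and the SPSS software named there can do both steps. The downsides are limited:

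- A linear T0 slope is assumed for a bounded integer score.
- Estimating the slope costs about 2% in variance when b is near 1 (factor 1 + 1/43 = 1.023).
- The residual test gives no confidence interval of its own, so the test and the estimate come from different models.

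A single primary time point, the future of the Kruskal-Wallis test and adjustment of the MotA-versus-CogA comparison are separate questions that this change does not depend on.

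### MMSE is the primary outcome, but the plan tests anodal against sham at both T1 and T2, each at an unadjusted 0.05, and never says which visit or what rule decides success

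*Combined protocol and SAP*

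**What the plan says.** Evaluation procedures names one primary outcome: "The primary outcome will be the Mini Mental State Examination (MMSE), used to assess global cognitive impairment". It attaches no visit to that outcome. The same section sets the schedule: "Patients will be evaluated before treatment (T0), immediately after treatment (T1), and at a one-week follow-up (T2".

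Statistical analysis compares the pooled anodal groups with the pooled sham groups by Mann-Whitney test, "comparing MotA+CogA versus MotS+CogS between T1 and T0 (T1-T0) and between T2 and T0 (T2-T0". The two change scores appear in one sentence with equal standing, and the MMSE is not singled out from the secondary measures. A second comparison follows the same pattern: "Further analysis will investigate differences in performance between the MotA and CogA groups from T1 to T0 (T1-T0) and from T2 to T0 (T2-T0". The only threshold for analysis is "The alpha level for significance will be set at $P < 0.05". The document contains no testing order, multiplicity adjustment, sidedness or definition of a positive trial.

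Three other statements bear on the point. The opening paragraph says "The aim of this study will be to evaluate the effectiveness of combining tDCS with motor or cognitive activities". The sample-size paragraph says "With an effect size of 1.15, an alpha of 0.01, and a power of 0.90, a total of 48 patients will be required". Participants says "Unbalanced randomization will be applied" without giving the ratio.

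**The concern.** At least three decision rules are compatible with this text: one visit decides, either visit is enough, or both visits are needed. They have different error rates and different power, and the plan chooses none of them. If T1 and T2 give different answers, the favourable one can be chosen once the data are known, and nothing in the plan would show that a choice had been made. A genuine positive finding would be open to the same suspicion. A reader cannot tell in advance which MMSE comparison decides whether tDCS worked.

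**Working it through.** **Inputs from the plan.** Two tests of the primary outcome (T1-T0 and T2-T0), each at 0.05; effect size 1.15; design alpha 0.01; power 0.90; total 48.

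**Assumptions, not in the plan.** Two-sided tests; correlation r of 0.5 to 0.9 between the T1 and T2 changes; pooled splits of 24 v 24, 32 v 16 and 36 v 12, because no ratio is given. Unbalanced refers to the four groups, so the pooled anodal and sham groups could still be equal.

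**1. The plan's 48.** The normal approximation, two-sided and 1:1, gives n per group = 2(2.576 + 1.282)² / 1.15² = 22.5, so 23, or 46 in total. A two-sided t-test needs 50 (power 0.897 at 24 v 24), a one-sided t-test 44, a two-sided Mann-Whitney test 52 and a one-sided Mann-Whitney test 46. The stated 48 lies among these, but its exact basis cannot be identified.

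**2. False-positive rate with no true effect.** Treat the two test statistics as bivariate normal with correlation r. Then P(either) = 1 − P(|Z1| < 1.96 and |Z2| < 1.96), P(both) = 0.05 + 0.05 − P(either), and P(visits disagree) = P(either) − P(both).

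| r | Either visit | Both visits | Visits disagree |
|---|---|---|---|
| 0 | 0.0975 | 0.0025 | 0.095 |
| 0.5 | 0.0907 | 0.0093 | 0.0815 |
| 0.8 | 0.0781 | 0.0219 | 0.0561 |
| 0.9 | 0.0704 | 0.0296 | 0.0407 |

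One named visit gives 0.05 whatever r is. At r = 0 the either-visit figure is 1 − 0.95² = 0.0975, which is the ceiling. With 0.025 at each visit, the either-visit rate is 0.0494 at r = 0 and 0.0362 at r = 0.9.

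**3. How often the rule would matter if tDCS works.** Simulated Mann-Whitney tests on integer changes, 48 analysed, effect 1.15 at T1, r = 0.5 and 0.9, each visit at 0.05:

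- Effect halves by T2 (0.575): the visits disagree in about 50-54% of trials (24 v 24 or 32 v 16). Success is 0.94-0.97 if either visit counts and 0.41-0.47 if both must.
- Effect persists at 1.15: the visits disagree in about 3-6% (24 v 24) or 5-9% (32 v 16), and both are significant in about 0.90-0.95.

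**4. Power of the remedies at effect 1.15, 48 analysed.** For one visit, the Mann-Whitney test is approximated by a noncentral t with sample sizes scaled by 3/π = 0.955. The noncentrality is 1.15 × √(0.955 × n1·n2/(n1+n2)). At 24 v 24 this is 1.15 × √(0.955 × 12) = 3.89, giving power 0.968 at 0.05. The ranges below combine this formula with the integer-score simulation; the last two columns are simulated.

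| Split | One named visit, 0.05 | At least one visit at 0.025, effect persists | At least one visit at 0.025, effect halves |
|---|---|---|---|
| 24 v 24 | 0.96-0.97 | 0.96-0.98 | 0.93-0.94 |
| 32 v 16 | 0.94-0.95 | 0.93-0.97 | 0.89-0.91 |
| 36 v 12 | 0.89-0.91 | 0.88-0.94 | 0.83-0.84 |

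**The case against.** The best reply is that this is a proof-of-concept pilot, that T1 comes first and T2 is called a follow-up, so T1 is naturally the main visit, and that no sentence says either visit would count as success. This is fair, and it lowers the stakes. It does not supply the rule. The plan also states an effectiveness aim, a primary outcome, a significance level and a sample size set for 0.90 power, and it gives the two change scores equal standing.

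A second reply is that the design alpha of 0.01 already allows for two tests. If 0.01 were applied at each visit, the either-visit error would indeed be at most 1 − 0.99² = 0.0199. But the plan does not link the 0.01 to multiplicity, and its stated analysis level is 0.05.

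A reader might also infer several stronger points that the documents do not support:

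- **That the trial's error rate is inflated to nearly 10%.** Inflation arises only if either visit counts. The 9.75% is a ceiling for uncorrelated tests, which is unlikely for changes measured a week apart from a shared baseline.
- **That the visits will disagree in half of trials.** That assumes the effect halves within a week, and the plan gives no figure on persistence. If the effect lasts, disagreement is uncommon.
- **That the 48 is wrong, or that the 0.01 v 0.05 mismatch underpowers the trial.** The test, sidedness and ratio behind the 48 are not given. Designing at the stricter level is conservative at or near equal allocation. At 36 v 12 the margin is gone (0.89-0.91).
- **That splitting alpha is unaffordable.** Single-visit power at 0.025 (0.938, 0.907 and 0.849 for the three splits) is close to a lower bound for a rule that needs only one visit.

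**Conclusion.** The concern holds as a missing decision rule for the primary outcome, and it should be fixed. The plan as written allows two attempts at the primary claim without saying whether both count. If either does, the false-positive rate is 7.0-9.1% for assumed correlations of 0.9 down to 0.5; naming one visit keeps it at 5%, and requiring both keeps it below 5%. These figures assume two-sided tests and cover only the MMSE comparison of anodal with sham, not the secondary outcomes or the MotA v CogA comparison. How much the gap matters in practice depends on whether the effect lasts to T2, which the documents do not address. The two alpha levels are a separate, minor point of clarity.

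**What to change.** Before results are seen, state the rule in one sentence. The preferred form is: the primary analysis is the MMSE change at one named visit (for example T1-T0), MotA+CogA against MotS+CogS, Mann-Whitney, two-sided 0.05; the change at the other visit is secondary. This needs no extra patients. If about 10% were lost (an assumption, since no dropout allowance is stated) and 43 were analysed, power would be about 0.94-0.95 (22 v 21), 0.91-0.92 (29 v 14) or 0.86-0.88 (32 v 11).

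The alternative is to keep both visits as primary, using Holm or 0.025 each, with success defined as at least one visit significant. For that definition the two procedures have the same power, because Holm also first requires the smaller p-value to be below 0.025. This option does well if the effect persists, but is tighter than the named visit under unequal allocation if the effect fades.

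Either way, the cost is that a result seen only at the non-primary visit, or one that misses the adjusted level, no longer counts as primary success.

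As a separate clarification, say which alpha applies, 0.01 or 0.05, and restate the sample-size sentence with the test, sidedness and allocation ratio actually used.
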